Game Changers: Pilot Intervention to Empower HIV Clients as Prevention Advocates in Uganda

November 13, 2018

PROTOCOL SUMMARY

1. Background and Rationale

Stagnant, high HIV prevalence in Uganda calls for innovative approaches to prevention. Uganda, as elsewhere in sub-Saharan Africa, has a generalized HIV epidemic with new infections caused by heterosexual sex (~80%) or mother-to-child transmission (~20%), and <1% due to homosexual sex, blood transfusions or other causes. HIV prevalence has stagnated at ~7% since 2005, with a continued annual incidence of about 130,000.

Empowering people living with HIV (PLWH) to be change agents for HIV prevention draws on the full armament of existing prevention paradigms. Prevention for Positives and Treatment as Prevention have targeted the risk and treatment behaviors of PLWH, but current paradigms do not take advantage of the potential for PLWH to be change agents for HIV prevention within their social networks. Receipt of HIV care often comes with renewed health and a sense of community and support from HIV-positive peers, and our research suggests that most HIV-positive clients actively encourage friends and family to seek HIV testing and care, and reduce risk behavior. Drawing on theoretical frameworks for network-based social influence, and established relevant interventions, this study will pilot test Game Changers - an intervention that aims to empower and mobilize PLWH to be agents for HIV prevention and behavioral change in their social networks.

2. Objectives

The primary objective of this study is to assess feasibility, acceptability, and preliminary intervention effects of the Game Changers Intervention on: a) protective behavior of PLWH (condom use, number of partners, engagement in HIV care, ART adherence); and b) diffusion of prevention messages across the network, as assessed by the content and extent of communication with network members about protective behaviors (condom use, number of partners, HIV testing, engagement in HIV care, circumcision), HIV disclosure, and HIV stigma.

3. Study Design

We will screen approximately 500 PLWH at the Infectious Disease Institute (IDI) clinic to arrive at a sample of 96 participants who will be randomized to intervention or wait-list control (each evenly stratified by gender). There will be 4 gender-specific intervention groups and one control. The intervention consists of 6 workshops, which will occur approximately every other week. Participants will be asked to complete a workshop evaluation form after each workshop. Participants will be interviewed at baseline, 3-4 months after baseline, and again 6-7 months after baseline. The wait-list control will receive the intervention upon completion of the final follow-up assessment has been completed by all intervention groups.

Participants will be asked to recruit 1-3 of their social network members to participate in three interviews. We expect to screen approximately 180 social network members to arrive at 90 participants.

4. Methods

Screening/Recruitment

There will be one screening/recruitment procedure for all PLWH participant-related procedures. The coordinator (who will be part of the clinic staff) will obtain the list of eligible clients scheduled for clinic visits during the recruitment period and will approach these individuals in the waiting room while they wait to see their provider to inform them of the study and assess their interest in participating. Alternatively, the coordinator will be at the clinic during days/times when potential participants are expected to be there. When clients are screened individually by the coordinator, they will be informed of the eligibility criteria and the legal risks of participation if they engage in same-sex sexual behavior or commercial sex work. Clients who express interest will be initially screened for age (to ensure they are 18 years of age or older), sex (to ensure adherence to the strata described above), length of time in care, and having disclosed serostatus to at least one person. Clients will then be given an information sheet and consent form that explains the project in detail. They will be given the option to provide signed consent to participate at the clinic that day, or to take the materials home and consider, with instructions to return the signed consent form to the coordinator if they are interested. This allows gay clients to withdraw their interest without disclosing their sexuality. Clients will be assured that all information collected is confidential, and no identifying information will be collected and stored unless the person is eligible and enrolls in the study.

Procedures

Participants will be randomized to be in the Game Changers program or in the wait-list control condition. The **Game Changers** program will consist of 6 workshops conducted by trained IDI personnel. Stigma reduction and self-acceptance, comfort and competence with HIV disclosure, and healthy, positive living, form the foundation for effective prevention advocacy, and are the focus of the initial workshops. With the foundation set by the first few workshops, the last few workshops provide participants with skills, confidence and support for engaging in prevention advocacy with members of their network, and with education about tailoring messages.

The 6 workshops will be implemented over about three months. Each workshop will last about 2 hours and will be facilitated by 1-2 trained counselors with experience conducting group trainings and working with people living with HIV. The workshops will be administered in a group format to facilitate an interactive social process, social reinforcement, modeling, role-

plays and other interactive components of skills building; groups are most effective in developing self-identity as members of a community in which members rely on each other for support. A workshop evaluation survey will be conducted at the conclusion of each workshop.

PLWH interview and social network assessments will be conducted by trained IDI personnel. The interview and social network assessment both will be administered in a single session in either English or Luganda as preferred by the participant. The first interview will last approximately 2.5 hours, and the second two interviews will last approximately 2 hours.

The interviews will collect information about participant demographics; engagement with HIV care, prevention advocacy; knowledge/beliefs about and adherence to HIV medication; HIV-related self-efficacy; HIV status disclosure; discrimination and stigma; social support; physical and mental health status; alcohol use; and relationship status and sexual behavior. During the social network assessment portion, participants will be asked to list 20 adults (18+ years) with whom they have had contact within the preceding year (e.g., friends, family, other community members). We will collect first name and last initial for each social network member to avoid the potential for confusing individuals who might have the same first and last initial, and to assist with linking network member data across assessments (to assess network change over time). For each social network member listed we will collect information about demographics; perceived serostatus; description of the relationship between the PLWH participant and the individual; PLWH participant's engagement in prevention advocacy with the individual; social support provided by the individual; and the individual's expression of HIV-related stigma. We will also ask for a description of how often individuals listed in the social network assessment interact with each other.

Interview data and social network assessment data will be collected using an offline version of EgoWeb. Hard and soft copies of raw data, including participant identifiable information will be kept at IDI, and only computer files with de-identified data will be kept at RAND. The IDI study coordinator will keep a linking file that matches study IDs with participant names. The linking file will be stored separately from research data. Interview and network assessment data will be exported to transmittable files (e.g., Excel), and then the study coordinator will remove identifying information and insert study IDs into this file prior to transmittal to RAND. The file will be transmitted to RAND via SFTP, after which it will be moved to a secure RAND server and accessible to authorized personnel only.

Social network member interviews will be conducted by trained IDI personnel. The interview will be administered in either English or Luganda as preferred by the participant. The first interview will last approximately 2 hours, and the second two interviews will last approximately

1-2 hours. These interviews will assess participants HIV protective behaviors (e.g., condom use) and receipt of prevention advocacy from the intervention participant.

Interview data will be collected using an offline version of EgoWeb. Hard and soft copies of raw data, including participant identifiable information will be kept at IDI, and only computer files with de-identified data will be kept at RAND. The IDI study coordinator will keep a linking file that matches study IDs with participant names. The linking file will be stored separately from research data. Interview data will be exported to transmittable files (e.g., Excel), and then the study coordinator will remove identifying information and insert study IDs into this file prior to transmittal to RAND. The file will be transmitted to RAND via SFTP, and will be accessible to authorized personnel only.

Focus groups will occur at the conclusion of the intervention, and topics will include participants' overall attitudes about the program, the facilitators, and different program activities, as well as how the program might be improved. We will conduct 5 groups, one for each intervention group, and 1 for the wait-list control group (after wait-list control participants receive the intervention).

The groups will be facilitated using a structured guide of topical areas and questions. Open-ended questions will be asked before probing questions to avoid biasing responses. The initial open-ended format allows for exploring new leads and related topics and generates rich personal narratives. Standard probes (verification; compare and contrast) will be used. Facilitator training will be conducted by [name] and [name], and will cover the discussion guide, sensitivity issues, and confidentiality. Each focus group will last ~60 minutes.

Note that participants may be called or texted as a reminder about the focus group session, if they provide their contact information to the interviewer.

Focus groups will be audio-recorded and transcribed. Before beginning the session, the facilitator will assign numbers to participants and ask that they use these numbers to identify themselves and others in the group when speaking. As a result, audio recordings of the focus groups will have no identifying information, will be stored on a password-protected, encrypted file, and then destroyed once a transcript has been completed (within one week of administration). Transcripts will be transmitted to RAND via SFTP, after which they will be moved to a secure RAND server and accessible to authorized personnel only. Any hardcopy notes or other files resulting from the focus groups will be retained by IDI.

Medical chart data obtained by RAND will include date of HIV diagnosis, last two CD4 counts and HIV viral loads, and prescribed HIV medication, and will be provided by the IDI clinic where PLWH participants receive care and will be recruited for this study (IDI is the main clinical

referral center for HIV at Mulago Hospital, and manages these medical charts). Hard and soft copies of raw data, including participant identifiable information will be kept at IDI, and only computer files with de-identified data will be kept at RAND. The IDI study coordinator will keep a linking file that matches study IDs with participant names. The linking file will be stored separately from research data. The study coordinator will remove identifying information and insert study IDs into this file prior to transmittal to RAND. The file will be transmitted to RAND via SFTP, after which it will be moved to a secure RAND server and accessible to authorized personnel only. Medical chart data will be merged with other datasets using the study ID.

Workshop evaluation surveys will be administered to participants by IDI personnel at the end of each workshop to elicit data on usefulness of the workshop, comfort with specific exercises, and ideas for improvement. No identifying information will be collected in this survey.

Survey data will be entered into a spreadsheet and transmitted to RAND via SFTP. If onsite data entry is not possible, scanned copies of the surveys will be transmitted to RAND via SFTP. Any hardcopy files resulting from the survey will be retained by IDI.

5. Statistical Analysis

We will primarily use an intent-to-treat approach, with secondary analyses involving study completers. In addition to comparing the arms at each time interval, we will apply generalized mixed models (linear for continuous or ordinal outcomes; logistic for binary outcomes) to our repeated-measures data to examine how intervention effects change over time, using an indicator for study arm, an ordinal indicator of time, and time by arm interaction to indicate whether change differs between the arms.

Aim 1: To assess feasibility and acceptance of the intervention, we will examine recruitment (# who sign up as interested in participating each recruitment day) and retention, workshop attendance (# who attend all workshops), and participant feedback elicited in the process measures (ratings of benefit; recommendation to peers). We will also compare the characteristics of the participants with that of the larger clinic population using routine data collected by IDI in order to assess the degree of selection bias caused by our recruitment strategy.

Aim 2: To assess preliminary intervention effects on the outcomes (protective behavior of the HIV-positive clients: condom use, number of partners, engagement in HIV care, ART adherence), and diffusion of prevention messages across the network (content and extent of communication with network members about protective behaviors, including condom use, number of partners, HIV testing, engagement in HIV care, circumcision; HIV disclosure; and HIV stigma), we will primarily use an intent-to-treat approach, with secondary analyses involving

study completers. In addition to comparing the arms at each time interval, we will apply generalized mixed models (linear for continuous or ordinal outcomes; logistic for binary outcomes) to our repeated-measures data to examine how intervention effects change over time, using an indicator for study arm, an ordinal indicator of time, and time by arm interaction to indicate whether change differs between the arms. A random-effects approach allows us to incorporate the heterogeneity among participants. We will use imputation for item nonresponse and account for non-random dropouts using logistic regressions that assign weights to retained participants that are inversely proportionate to the predicted probability of the participant being retained; if dropout is random, analyses will incorporate design effects when calculating standard errors and significance tests. With the intervention administered in groups, these analyses need to account for clustering of the data; however, the number of groups receiving the intervention is too small to reliably estimate the ICC to adjust standard errors; hence, we will use standard regression methods and explore the sensitivity of significance levels and conclusions to a range of plausible ICC values (.005 to .05) for the outcomes. We will also control for and examine interaction effects with intervention process variables (e.g., number of workshops completed), participant characteristics (e.g., ART status, gender, age), and alter characteristics (e.g., position in the network, HIV status, knowledge of ego's HIV status). This will enable us to address Aim 3, to explore the context of prevention advocacy, including differentiating types of alters who received more, versus less, prevention advocacy, as well as characteristics of participants who engaged in more prevention advocacy throughout the network, to a larger number of alters.

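### The feedback component of Aim 1 draws its only described ratings from people present at each workshop, so it may be biased, probably upward, and nothing described obtains the views of those who stopped coming

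*Combined protocol and SAP*

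**What the plan says.** Section 2 (Objectives) puts feasibility and acceptability in the primary objective. Section 5 (Statistical Analysis), Aim 1, lists the measures:

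- recruitment and retention: "we will examine recruitment (# who sign up as interested in participating each recruitment day) and retention";
- attendance: "workshop attendance (# who attend all workshops";
- feedback: "participant feedback elicited in the process measures (ratings of benefit; recommendation to peers".

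Section 4 (Methods), Procedures, describes one structured rating instrument: "Workshop evaluation surveys will be administered to participants by IDI personnel at the end of each workshop". Its purpose is "to elicit data on usefulness of the workshop, comfort with specific exercises, and ideas for improvement", and "No identifying information will be collected in this survey".

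There is also a qualitative source. "Focus groups will occur at the conclusion of the intervention, and topics will include participants' overall attitudes about the program", and "We will conduct 5 groups, one for each intervention group, and 1 for the wait-list control group". The text does not say whether people who stopped attending are invited.

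Interviews take place at baseline, 3-4 months and 6-7 months (Section 3). The interview topics listed in Section 4 include no rating of the programme. Section 5 plans inverse-probability weighting for dropout, but describes it under Aim 2 and does not mention these forms.

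**The concern.** A form handed out at the end of a session reaches only those in the room. Someone who leaves after workshop 1 or 2 because the programme was unhelpful or uncomfortable gives no later rating. If dissatisfied people are the ones who leave, average ratings rise as they go.

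With no described link to attendance, the analyst could not compare the early ratings of later leavers with those of stayers, or weight the ratings for who left. The plan already guards against related problems elsewhere: it checks selection at recruitment and models non-random dropout for the Aim 2 outcomes. The acceptability ratings have no equivalent step.

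The source of the ratings is also unclear. Aim 1 names ratings of benefit and recommendation to peers. The form is described as covering usefulness, comfort and improvements, so no described instrument clearly collects the recommendation item.

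At stake is how a measure within the primary objective is read. No acceptability threshold or test is stated, so no formal decision rule is affected.

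**Working it through.** The documents give no expected attendance, rating or acceptability threshold, so there is no figure to reproduce. All percentages below are assumptions.

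**Inputs.** Six workshops (Section 3). Let *s* be the share of the intervention arm who stay to the end, *p* the proportion of stayers who are favourable, *q* the proportion of leavers who are favourable, and *k* the number of sessions a leaver attends before stopping.

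**Value for the arm as randomised:** s·p + (1 − s)·q.

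**Case 1: only workshop 6 forms are used.** The forms show *p*, so the overstatement is (1 − s)(p − q).

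- s = 60%, p = 90%, q = 40%: the arm value is 0.6 × 90% + 0.4 × 40% = 70%. The forms show 90%, a gap of 20 points.
- s = 80%, same p and q: the arm value is 0.8 × 90% + 0.2 × 40% = 80%, a gap of 10 points.

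**Case 2: all six sets of forms are pooled and leavers rate the sessions they attended.** The forms show [6s·p + k(1 − s)·q] / [6s + k(1 − s)].

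- s = 60%, k = 2: (3.6 × 90% + 0.8 × 40%) / 4.4 = 81%, against 70%. The gap is about 11 points.
- s = 80%, k = 2: (4.8 × 90% + 0.4 × 40%) / 5.2 = 86%, against 80%. The gap is about 6 points.

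Pooling reduces the gap but does not remove it. In the first example leavers are 40% of the arm but supply 0.8/4.4 = 18% of the forms.

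**Range.** Overstatement in points under the Case 1 formula, with p = 90%:

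| Attending | q = 90% | q = 60% | q = 30% | q = 0% |
|---|---|---|---|---|
| 90% | 0 | 3 | 6 | 9 |
| 80% | 0 | 6 | 12 | 18 |
| 70% | 0 | 9 | 18 | 27 |

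The first column is the case where absence is unrelated to opinion. The sign can also reverse. At 80% attending, setting absentees to 0% and then 100% favourable puts the arm value between 0.8 × 90% = 72% and 72% + 20% = 92%, against 90% on the forms.

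**The case against.** A reader might infer that the whole Aim 1 result is biased upward. The documents do not support that. Recruitment, retention and attendance at all workshops are reported under the same aim, and one missed session already counts against the attendance measure. A programme that many abandoned would show up there. This stands, and it confines the point to the feedback component. Those counts still cannot separate dislike from transport, work or illness, and the attendance measure treats one missed session like leaving after the first.

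A reader might also infer that the forms cannot be linked to attendance at all. The text excludes identifying information, but elsewhere the protocol distinguishes that from study IDs, so a study ID on the form is not expressly ruled out. What can be said is that no link is described.

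Nor is the problem wholly undetectable. The number of workshops completed is a process variable in Section 5, and forms can be counted at each session. Those counts would show attrition, but not what the leavers thought.

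Three further objections have force:

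- Leavers do rate the sessions they attended, so the 20-point figure applies only to workshop 6 forms.
- The upward direction is an assumption. People may stop for reasons unrelated to their opinion of the programme.
- The focus groups are a second source, with reminders by call or text. They yield no rating with a denominator, however, and their coverage of people who stopped is not stated.

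Finally, it is tempting to make an interview rating the main acceptability result. Interviews are face to face with IDI personnel, at the clinic where participants receive care, and answers may be less candid than on an anonymous form. That objection stands: the interview items should sit alongside the forms and not replace them.

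**Conclusion.** The point holds for the feedback component of Aim 1 only. The one structured rating instrument described reaches those present at each session, no link to attendance is described, and no described instrument obtains ratings or reasons from people who stopped. The source of the peer-recommendation item is not identified.

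Upward bias is the more plausible direction but is not established. Its size depends on attendance and on leavers' opinions, and the documents give neither. With 60% staying and 90% against 40% favourable, it is about 11 points with pooled forms and two sessions per leaver, 20 points with workshop 6 forms alone, and nil if absence is unrelated to opinion. The plan as described could not tell which of these applies. The consequence is for interpretation of the ratings. The change is cheap enough that it should be made.

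**What to change.** 1. Add three items to the existing 3-4 month interview of everyone randomised to the intervention, including those who stopped attending: benefit, whether they would recommend the programme to peers, and the reason for any missed workshops. This also gives the recommendation measure a defined source.
2. Report these items alongside the session forms, with the number interviewed over the number randomised to the intervention.
3. For the session forms, report forms returned over number assigned at each workshop.
4. Keep the anonymous forms as a parallel source, for candour and for improving the workshops.

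The cost is a few more minutes in an interview of about 2 hours. Two limits remain: face-to-face answers may be less candid, and some people who leave the workshops may also miss the interview. The second is why the denominator in step 2 must be shown.

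### If ordinal time is one numeric score, the single time-by-arm term is close to a 6-7 month minus baseline contrast and cannot show how the effect changes after the workshops end; visit should be coded as a category

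*Combined protocol and SAP*

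**What the plan says.** The same model is given twice in section 5 (Statistical Analysis), in the opening paragraph and under Aim 2. It is a generalized mixed model (linear for continuous or ordinal outcomes, logistic for binary ones) "using an indicator for study arm, an ordinal indicator of time, and time by arm interaction to indicate whether change differs between the arms". Its purpose is "to examine how intervention effects change over time". The sentence opens "In addition to comparing the arms at each time interval, we will apply generalized mixed models", so separate comparisons of the arms by time are planned alongside the model.

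The timing comes from two other places. Section 3 (Study Design) says: "Participants will be interviewed at baseline, 3-4 months after baseline, and again 6-7 months after baseline". Section 4 (Methods, Procedures) says: "The 6 workshops will be implemented over about three months". Section 3 also keeps the controls untreated until the end: "The wait-list control will receive the intervention upon completion of the final follow-up assessment". Both follow-up visits therefore compare treated with untreated participants, one near the end of exposure and one about three months later.

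Section 5 does not say whether ordinal time is a single score or a set of visit categories. It names no leading time point, and it does not say whether the visit-wise comparisons or the interaction carries the conclusion.

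**The concern.** With one follow-up visit at about the end of the workshops and one some three months later, this design can ask whether an effect persists, fades or goes on growing. The plan gives that question to the interaction. If time is one score, the modelled arm difference must change by the same amount in each interval, and a straight line through three visits cannot separate those shapes. The trial could report no differential change when an effect was present at 3-4 months and had faded, or describe a stable effect as still growing. The visit-wise comparison could then point one way and the interaction another, with no stated rule for reconciling them.

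**Working it through.** The documents give no power, alpha, effect size, SD, visit correlation, allocation ratio or dropout rate, so there is no planned figure to reproduce.

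**Inputs from the documents:** three visits (baseline, 3-4 months, 6-7 months), workshops over about three months, 96 randomised.

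**Assumptions:** linear outcome with SD 1; random intercept (equal correlation r between visits); 48 per arm; two-sided alpha 0.05; illustrative effect 0.6 SD; r = 0.5 (range 0.3-0.7); clustering by workshop group ignored.

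**1. Weight of each visit in the interaction.** With complete data the slope weight at time t is (t - mean) / sum of (t - mean)². For scores 0, 1, 2 the deviations are -1, 0, 1 and their squares sum to 2, so the weights are -1/2, 0, +1/2. Multiplied by the span of 2 they are -1, 0, +1.

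For months 0, 3.5, 6.5 the mean is 3.333, the deviations are -3.333, 0.167, 3.167 and the sum of squares is 21.17. Multiplied by the span of 6.5, the middle weight is 0.167 × 6.5 / 21.17 = 0.05.

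| Times | Missing at last visit | Baseline | 3-4 months | 6-7 months |
|---|---|---|---|---|
| 0, 1, 2 | 0% | -1.00 | 0.00 | 1.00 |
| 0, 1, 2 | 20% | -1.05 | 0.10 to 0.11 | 0.95 |
| 0, 1, 2 | 30% | -1.09 | 0.17 | 0.91 |
| 0, 3.5, 6.5 | 0% | -1.02 | 0.05 | 0.97 |
| 0, 3, 7 | 0% | -0.95 | -0.10 | 1.04 |
| 0, 4, 6 | 0% | -1.07 | 0.21 | 0.86 |
| 0, 4, 6 | 30% | -1.13 | 0.40 | 0.74 |

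Zero weight is exact for equal spacing with complete data. Elsewhere the weight is usually small; the last row is the most extreme case examined.

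**2. What the line reports (scores 0, 1, 2, complete data).** The fitted line passes through the mean effect at the middle visit, with slope (e₂ - e₀)/2.

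| True effects | Mean | Slope | Fitted effects |
|---|---|---|---|
| Full fade (0, d, 0) | d/3 | 0 | 0.33d, 0.33d, 0.33d |
| Half fade (0, d, 0.5d) | 0.5d | 0.25d | 0.25d, 0.50d, 0.75d |
| Plateau (0, d, d) | 0.67d | 0.5d | 0.17d, 0.67d, 1.17d |

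A full fade leaves no interaction and shows up as a constant arm difference, present even at baseline. A half fade is drawn as a rise. A plateau is 33% too low at 3-4 months, 17% too high at 6-7 months, and appears to be growing.

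**3. Power, one slope term against two arm-by-visit terms (2 df).** The SE of an arm difference in change is √[2(1 - r) × 2/n] = √[2 × 0.5 × 2/48] = 0.204. For a 6-7 month effect of 0.6, z = 0.6/0.204 = 2.94 and the slope has power 0.84. For changes a and b at the two follow-ups, the 2-df noncentrality is n/[3(1 - r)] × (a² - ab + b²) = 32 × (a² - ab + b²). This is 32 × 0.36 = 11.52 for full fade and plateau, and 32 × 0.27 = 8.64 for half fade and steady rise.

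| True effects | Slope (1 df) | Visit category (2 df) |
|---|---|---|
| Full fade (0, 0.6, 0) | 0.05 | 0.87 |
| Half fade (0, 0.6, 0.3) | 0.31 | 0.75 |
| Plateau (0, 0.6, 0.6) | 0.84 | 0.87 |
| Steady rise (0, 0.3, 0.6) | 0.84 | 0.75 |

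Over r = 0.3 to 0.7 with complete data, full-fade power is 0.05 for the slope against 0.73-0.98 for 2 df; half-fade slope power is 0.24-0.48. With 20% missing at the last visit, full-fade slope power is only 0.06-0.07.

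**4. The visit-wise comparison.** A two-sample comparison at 3-4 months has SE √(2/48) = 0.204, so its power for 0.6 SD is also 0.84, whether or not the effect later fades.

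**The case against.** The strongest answer is in the same sentence of the plan: the arms are also compared at each time. A reader might infer that the trial would miss an effect that peaks and fades. The documents do not support that. The planned 3-4 month comparison would show it, with power 0.84 under the assumptions above; only the interaction would miss it. What those comparisons lack is a stated contrast. They are not described as comparing change from baseline within the model, and two separate comparisons give no estimate of the difference between the two effects.

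Second, ordinal time could mean ordered visit categories, and then the arithmetic above falls away. This is a fair point. The score reading is likelier, because the indicator and the interaction are both singular and the same sentence sends ordinal outcomes to linear models. It is not certain, and either way the coding needs to be stated.

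Third, a reader might infer that the model presumes an effect that keeps rising, or that decay is the expected shape. Neither is established. A straight line can go either way, and the slope test has the same power for a plateau as for a steady rise (0.84); the distortion there is in the fitted effects. The documents predict no shape. Advocacy skills come in the later workshops and message diffusion is an outcome, so continued growth after the workshops is credible.

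Finally, this is a pilot of preliminary effects with no confirmatory test. That limits the severity, though describing the course of the effect is the purpose the plan itself gives the model.

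**Conclusion.** The point holds for the interaction term, not for the analysis as a whole. With time as one numeric score, the term is essentially a 6-7 month minus baseline contrast: exactly so with equal spacing and complete data, and approximately so across most of the visit windows and dropout rates examined. Its expected value is then zero or near zero for an effect that fades fully, and it misdescribes a half fade and a plateau, so it cannot meet its stated purpose.

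The result rests on the score reading of an undefined coding, on linear outcomes and on a random intercept. The power figures also rest on the assumed 48 per arm, 0.6 SD and correlation. Logistic outcomes were not calculated and should behave similarly only in approximation. Severity is low to moderate: the visit-wise comparisons limit the harm, and the remedy uses data already being collected.

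**What to change.** In both places in section 5, the opening paragraph and Aim 2:

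- Enter visit as a three-level category with two arm-by-visit terms.
- Report, from that model, the arm difference in change from baseline at 3-4 months and at 6-7 months, and the difference between the two as the measure of persistence or decay, each with a confidence interval.
- State which contrast leads. The 2-df joint test may be added as the overall test of whether change differs between the arms.

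**Cost.** This is a wording change and one more parameter, with no new data or visits. If the 2-df test were the only test, power under a steady rise would fall from about 0.84 to 0.75 on the assumptions above. Keeping the 1-df 6-7 month contrast avoids that loss when data are complete and visits equally spaced, because it is then the same estimator as the slope times its span. The persistence contrast will be imprecise: under the same assumptions its SE is also 0.204, a 95% half-width of 1.96 × 0.204 = 0.40 SD, so it should be read as an estimate rather than a test.
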